2.3. Conclusion of the justification for the design of the study

There is a clear need for accurate pedicle screw placement when stabilizing the spine to prevent damage to important structures. Image-guided navigation has shown to result in significantly accurate pedicle screw placement. With Surgical Navigation we have a similar image-guided technique as described in literature, but using real-time video overlay to align an instrument with a planned path.

The positive results of pre-clinical testing and a clinical study with Surgical Navigation has provided confidence to perform a clinical study related to pedicle screw placement in humans to further evaluate Surgical Navigation. An observational pilot study using Surgical Navigation in a small group of patients undergoing a spine surgery involving pedicle screw placement is the next step in evaluating Surgical Navigation in clinical use. An observational, non-comparative study design has been chosen based on the primary objective of the study (i.e., to estimate the overall proportion of screws accurately placed with the research procedure). The outcome of the study will provide for estimation of the mean accuracy and confidence intervals for Surgical Navigation system. These result will be compared with earlier found results in the pre-clinical testing and may be used to design future studies.

Alternative studies design were evaluated but not chosen for the following reasons:

- Based on previous literature studies with procedure where pedicle screws are placed, there is a large variability between the accuracy of placing pedicle screws (mostly 68%-94%, one study even reported 28% accuracy for the standard of care method (See table 1 in the Investigator Brochure). This is due to differences in pedicle width in the different areas in the spine (cervical/higher thoracic versus lumbar) and deformation of spine (especially with scoliotic patients). So there is an expected difference for the outcome for pedicle screw placement accuracy between different subjects and between different screws within a subject.
- Randomizing treatment groups, during procedure, within a patient (i.e., left versus right side) for a paired study design that control for the between subject variability is cumbersome and may affect the

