6. STATISTICAL CONSIDERATIONS

6.1. Sample Size Justification

Mason et al (2014) reported on a meta-analysis of 30 studies evaluating screw placement using 2D, 3D, and conventional fluoroscopic image guidance systems. Using the conventional fluoroscopy, 2532 of 3719 screws were inserted accurately (68.1% accuracy); with 2D fluoroscopic navigation, 1031 of 1223 screws were inserted accurately (84.3% accuracy); and with 3D fluoroscopic navigation, 4170 of 4368 screws were inserted accurately (95.5% accuracy).

In a human cadaver study using Surgical Navigation system the accuracy was 85 % (95% CI of 72%, 95% and 74%, 96% using vertebrae within a cadaver as a cluster), compared to 64% (95% CI of 44%, 77%) for the conventional free-hand method. In another human cadaver feasibility study, 21 screws were placed using the fluoroscopy guidance system and another 21 screws using Surgical Navigation system. In 95% of insertions (20) the pedicle screws were placed in accordance with the predefined paths using the Surgical Navigation compared to 71% of the insertions with fluoro-guidance system.

IGT systems Best Status: Final	Clinical Investigation Plan Observational clinical study with Surgical Navigation to plan, position and check instrument placement for spine surgery interventions	XCY607-130099 2016 Sep 16 Revision: 6.0 Page 29 of 46
--	---	--

Assuming that the screw placement accuracy for this study will be similar to that observed in the cadaver study (i.e., 85%), a sample size of 240 screws will be required to estimate a 95% two-sided confidence interval so that the lower bound of the 95% CI is greater than the upper bound of the 95% CI observed for the cadaver study (i.e., 64% with upper bound of 95% CI of 77 with approximately 80% power (%) (i.e., approximately 5% Half Width). Assuming that the subjects will have 2 to 10 vertebrae's treated and the assumption that the majority of the patients will be scoliotic patients, approximately 15 to 25 patients will be needed to reach 240 screw placements.

Any deviation from the planned analysis described below will be documented with justification in the final clinical end report.

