6.5. Primary objective

Objective

The primary objective of this clinical investigation is to estimate the accuracy of pedicle screw placement using Surgical Navigation based on post-procedural CBCT:

Endpoint

The primary endpoint is the accuracy of screw placement. Screw placement will be evaluated using the slightly adapted Gertzbein⁴ classification for pedicle screw breach as follows:

- grade 0 = breach 0 mm
- grade 1 = lumbar and thoracic < 2 mm, cervical <1 mm breach distance
- grade 2 = lumbar and thoracic 2-4 mm, cervical 1-2 mm breach distance
- grade 3 = lumbar and thoracic > 4 mm, cervical >2 mm breach distance

Accuracy is defined as the proportion of screws with Gertzbein grade 0 or 1. The proportion of screws accurately placed will be estimated overall, and by region (e.g., cervical, lumbar, and thoracic).

In addition, the number of lateral or medial perforations, the distance of the longitudinal axis of the screw and the planned path at the smallest diameter of the pedicle (mm), and the largest distance between screw tip and planned target of screw (mm) will be reported.

See Appendix V: Background information primary objective for more information on the primary objective.

Analysis

The primary objective for this study is to estimate the overall proportion of screws accurately placed. All subjects who underwent treatment (ITT population) will be included in the primary efficacy analysis. Analysis will be performed assuming independence among different screws within a subject using Exact Clopper-Pearson 95% confidence interval. In addition, analysis will be performed using each subject as the unit for analysis. For this analysis, a two-sided 95% CI calculated for the accuracy of screw placement will be calculated using clustered binary data methodology as described by Zhou (2011)²⁹.

In addition, the proportion of screws accurately placed will be summarized by region (e.g., cervical, lumbar, and thoracic) and by grade 0-3. The 95% confidence interval will be presented.

IGT systems Best	Clinical Investigation Plan	XCY607-130099
Status: Final	Observational clinical study with Surgical Navigation to plan, position and check instrument placement for spine surgery interventions	2016 Sep 16 Revision: 6.0 Page 30 of 46

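### The primary analysis leads with a 95% CI that treats screws as independent and leaves the subject-clustered CI unranked, so the stated precision of the main estimate is likely to be too high

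*Protocol*

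**What the plan says.** Section 6.5 of the protocol (Analysis) sets the primary aim as estimating the overall proportion of screws with grade 0 or 1 among all treated subjects. It then gives two intervals for that proportion.

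- The first: "Analysis will be performed assuming independence among different screws within a subject using Exact Clopper-Pearson 95% confidence interval".
- The second: "In addition, analysis will be performed using each subject as the unit for analysis". Its two-sided 95% CI is to come from a cited method for clustered binary data.

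Nothing in 6.5 says which interval answers the primary objective.

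Other sections bear on the choice:

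- Section 2.3, when explaining the design: "there is an expected difference for the outcome for pedicle screw placement accuracy between different subjects and between different screws within a subject".
- Section 2.3, on use of the estimate: "These result will be compared with earlier found results in the pre-clinical testing and may be used to design future studies".
- Section 6.1, on the number of clusters: "approximately 15 to 25 patients will be needed to reach 240 screw placements".
- Section 6.1, on the sizing target, which refers to the conventional free-hand arm of a cadaver study with an upper limit of 77%: "so that the lower bound of the 95% CI is greater than the upper bound of the 95% CI observed for the cadaver study".
- Section 6.1, the only place where an interval with and without clustering can be compared: "95% CI of 72%, 95% and 74%, 96% using vertebrae within a cadaver as a cluster".

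**The concern.** If subjects differ in their underlying accuracy, two screws from the same subject are more alike than two screws from different subjects. The 240 screws then carry less information than 240 independent observations, and an interval computed as if they were independent is too short. Section 2.3 names two sources of variation. Only the between-subject part implies this correlation; differences between screws within a subject do not. The between-subject part is enough for the leading interval in 6.5 to conflict with the protocol's own expectation.

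This is not a detail left for a later analysis plan, because 6.5 itself fixes the independence assumption and the order of the two intervals. A reader given two unranked intervals is likely to take the first as the result. The estimate is meant to be set against pre-clinical results and may inform later studies, so overstated precision would carry forward.

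**Working it through.** **Inputs.** From 6.1: 240 screws, 15 to 25 subjects, assumed accuracy 85%, reference 77%, half width about 5 points. The average number of screws per subject is m = 240/15 = 16 to 240/25 = 9.6. The documents give no subject-level ICC, so 0.02, 0.05 and 0.10 are assumed.

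**The plan's own figure.** 85% of 240 is 204. Clopper-Pearson at 204/240 gives 79.8% to 89.3%, a half width of 4.7 points. This agrees with the stated half width of about 5, under independence. (The stated power of about 80% does not reproduce: exact power for a lower limit above 77% is 87.9%. That is a separate matter and nothing here depends on it.)

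**Approximate size of the effect.** Design effect = 1 + (m - 1) x ICC. Effective sample size = 240 / design effect. Coverage of a nominal 95% independence interval is about 2Φ(1.96/√design effect) - 1.

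| Subjects | ICC | Design effect | Effective screws | Approx. coverage |
|---|---|---|---|---|
| 15 | 0.02 | 1 + 15 x 0.02 = 1.30 | 185 | 91% |
| 15 | 0.05 | 1.75 | 137 | 86% |
| 15 | 0.10 | 2.50 | 96 | 79% |
| 25 | 0.02 | 1 + 8.6 x 0.02 = 1.17 | 205 | 93% |
| 25 | 0.05 | 1.43 | 168 | 90% |
| 25 | 0.10 | 1.86 | 129 | 85% |

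**Simulation.** Beta-binomial model, 20,000 trials per setting, 240 screws, 15, 20 or 25 subjects. Cluster sizes were equal, or unequal with 2 to 10 vertebrae per subject and an assumed two screws per vertebra. The text of the cited clustered method is not in the documents, so a ratio-estimator Wald form is assumed, with a normal (z) or t quantile. The last column is Clopper-Pearson on the effective sample size, with the design effect not below 1 and a t adjustment on subjects minus 1 degrees of freedom. Entries are coverage in %, as ranges over number of subjects and cluster pattern.

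| True accuracy | ICC | Clopper-Pearson, independence | Clustered, z | Clustered, t | Effective-n Clopper-Pearson |
|---|---|---|---|---|---|
| 85% | 0.02 | 91.7-93.3 | 92.2-93.4 | 94.1-94.5 | 96.6-96.9 |
| 85% | 0.05 | 86.6-90.0 | 91.9-92.8 | 93.3-94.2 | 95.6-96.4 |
| 85% | 0.10 | 77.3-85.8 | 90.5-92.7 | 92.7-94.0 | 95.1-96.1 |
| 95% | 0.02 | 92.9-94.5 | 89.6-92.2 | 92.4-93.1 | 96.5-98.2 |
| 95% | 0.05 | 88.3-91.9 | 88.5-90.9 | 90.9-91.7 | 96.1-97.3 |
| 95% | 0.10 | 80.4-87.8 | 85.8-89.8 | 87.7-90.8 | 94.9-96.4 |

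The 95% rows matter because 6.1 cites 95.5% accuracy (4170/4368) for 3D fluoroscopic navigation.

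**Do the two intervals read differently against 77%?** At true accuracy 85%, the independence interval and the z-form clustered interval fall on different sides of 77% in about 4-6%, 6-11% and 12-18% of simulated trials at ICC 0.02, 0.05 and 0.10. A few per cent of this is background. Even at ICC 0 the z form clears 77% in about 90% of trials against 88% for Clopper-Pearson, because it is then slightly narrower on average (half width 4.4-4.5 against 4.7 points).

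**The cadaver comparison.** Without clustering the width is 95 - 72 = 23 points; with clustering it is 96 - 74 = 22. There is no widening, but the cluster was the vertebra within a cadaver, so this does not tell how large the correlation between screws of one living subject is.

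**The case against.** The strongest reply is that the protocol already deals with clustering. It states the independence assumption openly, pre-specifies a subject-level interval for the same endpoint, and will report both, so neither can be chosen after the fact by leaving out the other. The study is a single-arm pilot with an estimation aim. Section 4.2 rules out pass/fail criteria (in its text on the secondary objectives), 6.5 states no success criterion, and 77% appears only in the sample-size rationale. All of this stands, and it limits the weight of the point.

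A second reply is that the planned clustered interval is not clearly better when accuracy is high. This also stands in part: at 95% accuracy and ICC 0.02, the assumed z form covers less often than Clopper-Pearson. It is a reason to correct the clustered interval for few clusters, not to lead with one that ignores clustering.

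A reader might go further and infer that, at the planned result of 204/240, the choice of main interval decides whether the lower limit clears 77%. The documents do not support that. Under the assumed Wald form the limit reaches 77% when the design effect equals 240 x (0.08/1.96)² / (0.85 x 0.15) = 3.14. That is an ICC of 2.14/15 = 0.142, 2.14/11 = 0.194 or 2.14/8.6 = 0.248 for 15, 20 or 25 subjects. With a t quantile the values are 0.108, 0.159 and 0.213. Over ICC 0.02 to 0.10 the lower limit stays at 77.9-80.1% (z) or 77.2-79.9% (t). A more conservative small-sample interval would cross earlier, but that would not be a comparison of the two intervals the protocol plans.

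**Conclusion.** The point holds as one about stated precision. Section 6.5 leads with an interval whose assumption conflicts with the expectation in 2.3, and it does not rank the subject-clustered interval that would respect that expectation. At 85% accuracy the loss of coverage is small at ICC 0.02 (about 92-93%) and material at 0.05 (87-90%) and 0.10 (77-86%). These sizes rest on assumed ICCs, a beta-binomial model and 15 to 25 subjects.

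The point estimate is unchanged, provided the clustered method uses the same pooled proportion. No decision rule is affected. Nor should the point be read as saying that the study would miss its 77% reference: the two planned intervals disagree on that in a minority of simulated trials, and not at 204/240 over the ICC range considered. It is worth correcting because the remedy uses an analysis already planned and costs almost nothing.

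**What to change.** In 6.5, state that the subject-clustered 95% CI is the primary interval for overall accuracy, and that Clopper-Pearson under independence is a sensitivity result.

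Add that the clustered interval will carry a small-sample correction, because there are only 15 to 25 clusters and accuracy may be near 95%. Possible forms are a t quantile on subjects minus 1 degrees of freedom, or Clopper-Pearson on the effective sample size with the design effect not below 1. In the simulations the t quantile helps only partly at 95% accuracy, while the effective-sample-size form covers about 95% or more throughout. The exact form can be left to the statistical analysis plan, to be settled before the data are seen.

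Cost: one or two sentences and no new data. The primary interval becomes wider. With the effective-sample-size form at 85% accuracy, the mean width rises from about 9.4 points to 10.9-12.0, 11.8-13.7 or 13.4-16.4 at ICC 0.02, 0.05 or 0.10. If there is no correlation at all, it is 10.4-10.9 points wide and somewhat conservative (about 97-98% coverage).

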6.6. Secondary objectives

6.6.1. Secondary objective: Procedure Time

Objective

To estimate the procedure time.

Endpoint

Besides the procedure time, also the time for preparation steps will be measured (see Table 4 for more specification).

Table 4: Time measurement

Endpoint	Measured by the time between
Total preparation time	Nurse in room to prepare room – Time-out
Preparation time before patient on table	Nurse in room to prepare room – Patient on table
Patient preparation time	Patient on table-Start anesthesia
Anesthesia time	Start anesthesia-End anesthesia
Patient preparation after anesthesia + use system for patient preparation	End anesthesia-Time-out
Procedure time	Incision time - Wound closure

Analysis:

Summary statistics will be calculated using Kaplan-Meier procedure.

6.6.2. Secondary objective: Time to insert a pedicle screw

Objective

To estimate the average time to insert a pedicle screw.

Endpoint

The time to insert a screw is calculated from:

- Start time of the CBCT to plan the path until last screw placed, divided by the number of screws.
- Start time from choosing the path to place the first screw until last screw placed, divided by the number of screws

The first represent the time it takes to place a screw taking into account the path planning and the second represent just the time it takes to place a screw during the live guidance work step. Time points are logged via the Surgical Navigation.

Analysis

Summary statistics will be calculated using Kaplan-Meier procedure.

6.6.3. Secondary objective: Length of hospital stay

Objective

To estimate the length of hospitalization (LOH)

Endpoint

The endpoint is length of hospitalization. This is calculated by the day of procedure until hospital discharge in days.

Analysis.

Summary statistics will be calculated using Kaplan-Meier procedure.

6.6.4. Secondary objective: System usability

Objective

Collect System Usability Scale (SUS) and assess the clinical workflow related to easiness to work, image quality, real-time image update, preparation of patient tracking, confidence in image guidance, access

IGT systems Best Status: Final	Clinical Investigation Plan Observational clinical study with Surgical Navigation to plan, position and check instrument placement for spine surgery interventions	XCY607-130099 2016 Sep 16 Revision: 6.0 Page 31 of 46
--	---	--

planning, 3D segmentation, motion compensation, identify unknown potential use errors and evaluate risk controls.

Endpoint

The endpoint is System Usability Scale measured at the end of the study. Furthermore the clinical workflow will be described.

All users that entirely completed the SUS questionnaire will be included in the analysis.

Analysis

The SUS scores of each respondent will be categorized according to the SUS score. Calculation of the scoring SUS will be done according to the following principle:

- For odd items: subtract one from the user response.
- For even-numbered items: subtract the user responses from 5
- This scales all values from 0 to 4 (with four being the most positive response).
- Add up the converted responses for each user and multiply that total by 2.5. This converts the range of possible values from 0 to 100 instead of from 0 to 40.

A SUS score above a 68 would be considered above average and anything below 68 is below average.

6.6.5. Secondary objective: Patient Dose

Objective

To estimate radiation dose (Dose Area Product (DAP) and Air Kerma (AK)) delivered to patient for:

Total procedure

- a) During preparation and acquisition of CBCT for path planning
- b) During screw/instrument placement (using fluoro).
- c) During preparation and acquisition of CBCT for confirmation
- d) Average procedure dose per planned path

Endpoint

The endpoint is Radiation Dose (DAP and AK) delivered to the patient:

- a) For Total procedure (including CBCT and fluoro)
- b) During preparation and acquisition of CBCT for path planning
- c) During screw/instrument placement (using fluoro) (DAP and AK and fluoro time).
- d) During preparation and acquisition of CBCT for confirmation
- e) Average procedure dose per planned path. Calculated based on dose described at b) and c) divided by the number of screws. Average procedure dose per planned path will also be reported per region (e.g. cervical, thoracic and lumbar)

Analysis

All subjects who underwent the procedure will be included in this analysis.

Radiation dose will be summarized using descriptive statistics. Mean, median, standard deviation and 95% confidence interval for the mean will be presented.

6.6.6. Secondary objective: Occupational dose

Objective

- 11) To estimate the total radiation dose (effective dose) received by operator, if DoseAware Xtend is available.

Endpoint

The endpoint is occupational dose measured via DoseAware Xtend. DoseAware Xtend is a CE labeled device. DoseAware Xtend measures real-time dose for the operator in the interventional suite via the use of Personal Dose Meter (PDM). The PDM is worn by the operator. This badge measures scatter radiation and transmits this information.

Analysis

This objective will only be done when DoseAware Xtend is present at a site.

IGT systems Best Status: Final	Clinical Investigation Plan Observational clinical study with Surgical Navigation to plan, position and check instrument placement for spine surgery interventions	XCY607-130099 2016 Sep 16 Revision: 6.0 Page 32 of 46
--	---	--

Occupational dose will be summarized using descriptive statistics. Mean, median, standard deviation and 95% confidence interval for the mean will be presented.

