 - d. During preparation and acquisition of CBCT for confirmation
 - e. Average procedure dose per planned path
- 6) To estimate the total radiation dose (effective dose) received by operator, if DoseAware Xtend is available.
- 7) To describe procedure related complications
- 8) Report all adverse events
- 9) Report all adverse device effects
- 10) Report all device deficiencies that could have led to a serious adverse event

Primary and secondary endpoints

The primary endpoint of the study is accuracy.

- 1) This is measured according to an adapted version of the in literature reported classification method by Gerztbein, so that it includes distance of breaches applicable for cervical region besides the lumbar and thoracic region.

Furthermore, accuracy will also be reported by direction of breach (lateral/medial), and distance between planned path and screw in smallest area of the pedicle (mm) and the distance between screw tip and planned target of screw (mm).

Secondary endpoints are:
Procedure time, time to insert a pedicle screw, Length of hospital Stay, System Usability Score, patient radiation dose (DAP and AK and fluoro time), occupational radiation dose (effective dose), procedure related complications, adverse events, adverse device effects, device deficiencies that could have led to a serious adverse event.

Main inclusion criteria

- Subject will be undergoing a spine surgery with pedicle screw placement
- Subject is 16 years of age or older
- Subject is able to give informed consent

Main exclusion criteria

- Subject participates in a potentially confounding device or drug trial during the course of the study.
- Subject meets an exclusion criteria according to national law (e.g. pregnant woman, breast feeding woman)

No. of subjects

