4.2. Secondary objective(s)

The secondary objectives are:

- 1) To estimate the procedure time.
- 2) To estimate the average time to insert a pedicle screw.
- 3) To estimate the length of hospitalization (LOH)
- 4) Collect System Usability Scale (SUS) and assess the clinical workflow related to easiness to work, image quality, real-time image update, preparation of patient tracking, confidence in image guidance, access planning, 3D segmentation, motion compensation, identify unknown potential use errors and evaluate risk controls.
- 5) To estimate radiation dose (Dose Area Product (DAP) and Air Kerma (AK)) delivered to patient for:
 - a. Total procedure
 - b. During preparation and acquisition of CBCT for path planning
 - c. During screw/instrument placement (using fluoro).

IGT systems Best Status: Final	Clinical Investigation Plan Observational clinical study with Surgical Navigation to plan, position and check instrument placement for spine surgery interventions	XCY607-130099 2016 Sep 16 Revision: 6.0 Page 25 of 46
--	---	--

- d. During preparation and acquisition of CBCT for confirmation
- e. Average procedure dose per planned path
- 6) To estimate the total radiation dose (effective dose) received by operator, if DoseAware Xtend is available.
- 7) To describe procedure related complications
- 8) Report all adverse events
- 9) Report all adverse device effects
- 10) Report all device deficiencies that could have led to a serious adverse event

The objectives are descriptive in nature and are intended to provide additional information. There will be no pass or fail criteria.

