5.5.1. Maintenance and calibration

The equipment relevant for the dose measurements during the clinical investigation are the Allura and DoseAwareExtend. Allura is calibrated at the time of installation and mostly after one year. DoseAwareExtend is calibrated once before providing it to the hospital. Since the duration of the study is expected to be less than one year after installation, both will not be monitored for calibration during the course of the study.

The optical cameras and the X-ray system in the Allura system will be calibrated during the installation in the hospital. Regular check will be performed by trained Philips personnel during the clinical study if recalibration of the camera and X-ray system alignment is needed.

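### The operator endpoint is named effective dose, but section 6.6.6 measures and summarises only a personal dose meter's scatter reading, with no conversion and no wearing position stated

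*Protocol*

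**What the plan says.** The objective in Protocol section 4.2 reads: "To estimate the total radiation dose (effective dose) received by operator, if DoseAware Xtend is available". The summary repeats it among the secondary objectives, and so does the objective paragraph of section 6.6.6. The summary's list of secondary endpoints uses the same label: "occupational radiation dose (effective dose".

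The endpoint paragraph of section 6.6.6 is worded differently: "The endpoint is occupational dose measured via DoseAware Xtend". It presents the instrument as a Personal Dose Meter that gives the operator's dose in real time. On where the meter sits, the paragraph offers no more than "The PDM is worn by the operator". On what the meter detects, it has one sentence: "This badge measures scatter radiation and transmits this information". The analysis paragraph says "Occupational dose will be summarized using descriptive statistics" and lists mean, median, standard deviation and a 95% confidence interval for the mean.

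Two other sections mention the device. Section 5.4 says that occupational dose data come from DoseAware Xtend if the hospital has it. Section 5.5.1 deals with calibration only: "DoseAwareExtend is calibrated once before providing it to the hospital".

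**The concern.** Effective dose is a tissue-weighted quantity for the whole body. It is always estimated, never read directly. A badge responds to scatter at the point where it is worn. That reading becomes an estimate of effective dose only through a conversion that assumes a known wearing position, including whether the badge sits in front of or behind any protective shielding. The Protocol gives the label but neither of the two things that would justify it.

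What is at stake is the meaning of one reported number. Section 4.2 describes the secondary objectives as descriptive, with no pass or fail criteria, so for this endpoint the labelled mean and its interval are the whole result. Section 15 states an intention to publish. A reader who sees effective dose would take it as such and could set it beside effective-dose figures from elsewhere, although the measurement described does not support that.

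**Working it through.** No arithmetic applies. The Protocol gives no operator-dose figure, conversion factor, precision target or sample size for this endpoint. The check is to set every place that names the quantity beside every place that says how it is obtained.

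| Place in the Protocol | What it gives |
|---|---|
| Summary, secondary objective 6 | Quantity: effective dose |
| Summary, secondary endpoints | Quantity: effective dose |
| Section 4.2, objective 6 | Quantity: effective dose |
| Section 6.6.6, objective | Quantity: effective dose |
| Section 6.6.6, endpoint | Quantity: occupational dose as measured by the device. Instrument: Personal Dose Meter responding to scatter |
| Section 6.6.6, analysis | Descriptive summary of occupational dose |
| Summary study procedures and section 5.4 | Source of the data: DoseAware Xtend |
| Section 5.5.1 | Calibration before delivery; nothing on deriving a dose quantity |

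1. *Is the label a single slip?* No. It appears in all four places that state the objective or list the endpoint.
2. *Does any section convert the reading to effective dose?* No. The analysis paragraph goes straight from the device's dose to summary statistics.
3. *Does any section fix where the badge is worn, or its relation to shielding?* No. Section 6.6.6 says only that the operator wears it.
4. *Does the Protocol elsewhere name a dose by what is measured?* Yes. Section 6.6.5 states patient dose as Dose Area Product and Air Kerma and does not relabel either as effective dose. The operator endpoint departs from the practice of the section just before it.
5. *Can the gap be closed at analysis?* Only in part. A conversion formula can be added later. A wearing position that was neither fixed nor recorded at the procedure cannot be recovered.

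The objective and the measurement in section 6.6.6 therefore name different quantities, and nothing in the document links them.

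**The case against.** The strongest reply is that the operative text is already right. The endpoint and analysis paragraphs of section 6.6.6 refer to occupational dose measured by the named device and do not use the words effective dose. On this view the fault is a loose parenthesis in the objective and the endpoint list. This stands as a limit on severity: nothing says that the published table must carry the objective's label. It does not remove the mismatch, because the objective and the endpoint list are what a report is normally written against, and both name the wrong quantity.

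A second reply is that the statistical analysis plan or the device's instructions, neither of which is shown, may supply the conversion and the wearing position. That is possible for the conversion, and the verb in the objective, to estimate, leaves room for it. The Protocol also does not say in which dose quantity the device reports. Wearing position, however, is a data-collection matter, and the Protocol neither fixes nor records it nor points to a document that does.

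A reader might go further in three ways that the documents do not support.

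- *A multiplicative bias.* One could assume a transmission for a lead apron, invert it, and say that the mean and both confidence limits are inflated by that factor. The Protocol mentions no apron. The ratio would compare the badge with the shielded trunk, not with effective dose, which also includes unshielded tissue. It would apply only if the badge were worn outside the shielding, which is not stated.
- *A single badge, or mixed positions that inflate the spread.* The singular wording suggests one meter, but the number is not stated, and nothing indicates that positions would vary.
- *A false conclusion on staff safety.* The Protocol plans no comparison of operator dose with limits or with other studies.

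**Conclusion.** The point holds as a mismatch between name and measurement. The objective promises effective dose, while the endpoint and analysis deliver a Personal Dose Meter reading of scatter, without a conversion or a stated badge position. If it is reported under the objective's label, the result is misnamed.

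Neither the size nor the direction of the difference from effective dose can be derived from the documents. The conclusion rests only on the Protocol's wording and on the definition of effective dose as a weighted whole-body quantity.

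Severity is low. This is the sixth of ten secondary objectives, it is descriptive, and it is conditional on DoseAware Xtend being available. It does not affect the primary accuracy estimate or the 240-screw target. It does change what can be concluded about operator exposure.

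**What to change.** - In the summary (objective 6 and the endpoint list), in section 4.2 and in the objective of section 6.6.6, replace effective dose with *operator dose as measured by the DoseAware Xtend Personal Dose Meter, per procedure*. The last two words also state the unit of summary, which the request for a mean and standard deviation implies but does not give.
- In section 6.6.6, state that one badge position, including its relation to any shielding, is used for all procedures, and record it in the case report form.
- Keep the term effective dose only if a conversion tied to that position is stated or cited.

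The cost is a change of wording, one recorded item per procedure and a less ambitious endpoint label. If procedures have already taken place, rename the endpoint and report the badge position as known or unknown for those cases.
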